### 3. Abstract:

Participant engagement/attendance in existing extended-care interventions remains suboptimal, limiting effectiveness for long-term weight loss maintenance. We propose to evaluate a method for providing phone-based extended-care intervention *adapted to participant needs* (e.g., when participants are at "high risk" for weight regain as assessed by a predictive algorithm). We propose to conduct a randomized controlled trial assessing the impact of phone-based extended care delivered on an *ADAPTIVE* (only when indicated via our algorithm or when requested in-app by participants) vs. *STATIC* (pre-scheduled, once-per-month frequency used in existing extended-care programs) schedule on weight loss maintenance. As we propose to study weight loss *maintenance*, a key design consideration was to only randomize participants who have been successful with initial weight loss.¹ Similar to existing maintenance trials,²₃³ we will provide participants with an initial group-based gold-standard behavioral weight management program and then randomize participants who successfully achieve a clinically-significant weight loss between baseline and Month 4 (defined by the Institute of Medicine⁴ as a reduction in weight of ≥ 5% from baseline).

# 4. Background:

Obesity remains a substantial public health challenge in the United States. While behavioral lifestyle interventions have been demonstrated to produce weight losses of 8-10% in adults with overweight and obesity, long-term outcomes are suboptimal. Following the end of initial treatment, individuals typically regain 1/3 to 1/2 of lost weight within a year and gradually return to baseline weight in 3-5 years. Research has demonstrated, however, that individuals who are able to continue to adhere to weight management behaviors can successfully maintain their weight loss long-term, implicating non-adherence to the eating and activity changes that produce weight loss as the primary mechanism for this weight regain.

As a result, current clinical guidelines now conceptualize obesity within a chronic disease "continual care" model, necessitating long-term treatment provision. Existing "extended-care" programs typically provide long-term support via monthly sessions (delivered in-person or via telephone) and have demonstrated significant improvements in adherence to behavior change and less weight regain compared to no-contact control. While these effects have been *statistically significant*, the impact of existing programs on weight regain has been *modest* (around 1.5 kg less regain vs. control at 24 months) and there tends to be high individual variability in response to treatment.

A key challenge to the effectiveness of extended-care programs has been continued participant engagement, typically operationalized as session attendance. Attendance has been consistently associated with long-term weight loss maintenance;  however, attendance at monthly extended-care sessions tends to be poor and declines over time.  The once-per-month, static treatment schedules of existing programs may contribute to these suboptimal outcomes.  Under this schedule, a participant experiencing a small lapse (e.g., failing to self-monitor dietary intake for several days) may not receive additional support for several weeks, by which time they may be experiencing a larger lapse (e.g., complete abandonment of self-monitoring and former dietary changes) and weight regain. Importantly, this cycle may result in participant disengagement and avoidance of treatment sessions due to feelings of frustration, shame, or embarrassment.  In contrast, tailoring intervention delivery such that extended-care sessions are provided when individuals are at "high risk" for weight regain offers potential to disrupt this cycle and significantly improve program engagement, adherence to program goals, and long-term weight maintenance outcomes.

[name] is currently PI of a NIDDK-funded grant (R21DK109205) aimed at identifying and characterizing "high risk" periods of weight regain. For this project, [name] and [name] (Co-I) first developed longitudinal change point mixture models to model the trajectory of weight loss and regain in 75 adults with overweight and obesity who took part in a 12-week Internet-based weight management program^20 followed by a 9-month maintenance observation period during which no additional intervention contact was provided. Next, longitudinal multilevel models were used to identify factors proximally (on a week-to-week basis) associated with weight regain after initial weight loss. During the full study year (including the 9-month maintenance period), participants used a study website each week to self-report the number of days they monitored their weight, dietary intake, and total minutes of physical activity and completed an 11-item questionnaire asking them to rate, on 7-point Likert scales, factors that had been hypothesized previously to be associated with weight regain (e.g., positive mood, negative mood, stress, hunger, boredom with weight control efforts, temptation to eat foods not on their plan, temptation to skip planned physical activity, the degree to which physical activity choices were consistent with weight loss goals, the amount of effort that it took to stay on track, and the importance of staying on track, compared to other demands in life during the previous week). In a sub-sample of participants from the initial dataset who had successfully lost ≥ 5% of their baseline weight during the initial 12-week intervention (n=46), these results were used to fit regression tree models. 21,22 These models were developed using R^23 package rpart,  using trimming methods proposed by Brieman,  and predicted weight change the following week as a continuous response variable.

Drs. [name] and [name] evaluated the optimized model in a test dataset consisting of the remaining 28 study participants who continued to submit data during the 9-month maintenance period but

whose data were not used to develop the predictive algorithm. In this separate test dataset, the algorithm demonstrated a sensitivity of 82.0% and a specificity of 30.4%. Taken together, these promising results suggested two key implications: 1) that weight regain can be reliably modeled and predicted, and 2) that this optimized predictive algorithm demonstrated good performance both in the initial training and separate testing datasets.

In the current study, we propose to evaluate an innovative method of providing phone-based extended-care treatment *adaptive to participant needs*. The proliferation of smartphones and mHealth apps has allowed for the development of new, adaptive treatment models aimed at providing intervention when it is needed most. Monitoring early signals of weight regain via an mHealth app will allow us to tailor intervention delivery at a previously-impossible level, via a method that is convenient and acceptable to participants. The dataset resulting from the current trial will be unique in terms of both *scope* and *resolution*, allowing us to build innovative behavioral models to inform future just-in-time adaptive intervention development.

# 5. Specific Aims:

**Aim 1:** Test the hypothesis that *ADAPTIVE* participants will experience significantly less weight regain than *STATIC* participants between Month 4 (randomization) and Month 24.

**Aim 2**: Test the hypothesis that, compared to *STATIC*, a significantly greater proportion of *ADAPTIVE* participants will maintain clinically significant (≥ 5% from baseline) weight losses at Month 24.

**Exploratory Aims:** We propose to 1) use daily weight data collected via our mHealth app to model differences in weight trajectories between groups; 2) investigate potential treatment mediators (e.g., treatment engagement/session attendance and adherence to diet, physical activity, and self-monitoring goals); 3) use the rich dataset collected via our mHealth app to develop dynamic models of weight loss/regain and to investigate additional proximal predictors of weight-related behaviors, identifying potential decision points and tailoring variables for future just-in-time adaptive intervention development.

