Participants will be asked to self-monitor weight daily, using a study-provided BodyTrace scale. Participants will be asked to self-monitor caloric intake and physical activity via the commercial FatSecret mobile app (provided free of charge to participants). This application can be accessed by participants via web (https://www.fatsecret.com/) or via smartphone application. At the first study intervention session, participants will be asked to download this application on their mobile devices and will be guided on how to set up accounts using either their preferred email address or a study-generated email address with no direct link to identifiable information. Participants will then be shown how to use this application to record their body weight, physical activity, and caloric intake each day. Participants will also be given guidance on how to protect their privacy and confidentiality using study devices and smartphone applications (e.g., suggesting using device encryption, using secure passwords and setting up automatic lock screens, and avoiding submitting personally-identifiable information through the applications).

**Randomization.** Participants who successfully achieve weight losses of  $\geq 5\%$  of initial body weight during the initial 16-week weight loss intervention (defined as change in assessment-measured body weight from Month 0 to Month 4) will be eligible for randomization for the maintenance program. After determining eligibility, participants will be randomized using a 1:1 allocation scheme by the study statistician ([name]), stratified by initial weight loss (due to the known association between initial weight loss and longer-term maintenance,  $^{32,33}$  participants will be categorized by whether initial weight loss was  $\geq 10\%$  or < 10%). Participants will be notified of their inclusion/exclusion and asked to return for one in-person study visit to be informed of their randomization (see full description below). This process will take place by phone if social distancing procedures are in effect.

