## Statistical Design and Power

The primary outcome for the proposed trial will be weight change from Month 4 to Month 24. This variable will be continuous, and analyses conducted during our team's previous trials have demonstrated that weight change can be well modeled using a normal distribution.³ Thus, standard parametric techniques will be used. A longitudinal mixed model will be used to analyze the primary aim data, using treatment condition and time since study start as fixed effects. One primary contrast of interest will be tested for significance: weight regain between Month 4 and Month 24 in the *ADAPTIVE* vs. *STATIC* treatment conditions. Fixed effects will include randomization condition, time since study start, and initial intervention weight loss (as a binary variable representing whether initial weight loss was ≥10% or <10%, used to stratify randomization). Sensitivity analyses will be conducted to assess robustness of results under alternative assumptions related to missing data (including a missing not-at-random approach assuming that individuals who discontinue participation in the study prior to Month 24 regained an average of .3 kg/month, up to baseline weight³,54,55).

The secondary outcome for the proposed trial will be the proportion of individuals in each group maintaining a clinically-significant ( $\geq 5\%$  weight loss from baseline/Month 0) at Month 24. Percent change will be calculated from assessment weights at Month 0 and Month 24, and participants will be categorized dichotomously as having weight losses at Month 24 of  $\geq 5\%$  or < 5% from baseline. Difference in proportion of participants maintaining a  $\geq 5\%$  weight loss will be assessed using a two-tailed z-test for independent proportions.

As an exploratory aim, we intend to compare weight loss trajectory over time between the two groups. For this, we propose to use longitudinal mixed-effects modeling and the growth curve modeling to analyze weight change data observed at several different time points, where the within-subject data correlated is accommodated by the random-effects terms included in the longitudinal mixed-effects model and by a general covariance matrix in the growth curve model. These analyses will demonstrate differences in weight change between participants in the

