*ADAPTIVE* and *STATIC* groups over time. Changes in dietary intake, physical activity, and self-monitoring adherence over time will be assessed using multilevel models for repeated measurements. Potential treatment meditators (e.g., intervention engagement, operationalized as the proportion of possible extended-care sessions attended, adherence to self-monitoring, and changes in dietary intake/physical activity) will be assessed using bootstrapping to estimate confidence intervals around indirect effects. Finally, the rich dataset collected via MyTrack+ (including time-stamped self-monitoring data (including not only frequency counts of self-monitoring behavior but also daily weight, caloric intake, and physical activity data) and ecological momentary assessment questionnaire data collected over a full two year study period) will be used to examine proximal predictors of change in weight and weight-related behaviors. Following the pragmatic framework developed by Nahum-Shani and colleagues, we propose to build dynamic models of weight loss and weight regain, identifying key tailoring variables and potential intervention options for future just-in-time adaptive interventions for weight loss maintenance.

The most recent clinical guidelines for the treatment of obesity (released as a joint report by the American College of Cardiology [ACC], American Heart Association [AHA] and The Obesity Society [TOS]) $^{10}$  define 2.5 kg as the *minimal* amount of weight loss associated with lowered risk of type 2 diabetes, and further note that weight losses of this magnitude are associated with modest improvements in triglycerides, and modest reductions in blood pressure. Thus, similar to previous weight management trials powered to detect this smallest clinically-meaningful difference, $^{3,28}$  sample size for the primary aim analysis was selected to provide a statistical power of .90 to detect a difference in weight change of  $2.5 \pm 5.5$  kg between groups from Month 4 to Month 24. This resulted in an estimated 206 participants (103 participants per group). With SDs of 5.0 and 6.0, estimated power would be .946 and .845, respectively. Assuming a retention rate of 80% at Month 24, 258 participants would need to be randomized at Month 4.

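### The exploratory mediation analysis states no pre-randomization adjustment, so for attendance and self-monitoring adherence a stable adherence trait can pass as mechanism if ADAPTIVE shifts the mediator

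*Combined protocol and SAP*

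**What the plan says.** Section 5 (Specific Aims) lists, under the exploratory aims, a plan to "investigate potential treatment mediators (e.g., treatment engagement/session attendance and adherence to diet, physical activity, and self-monitoring goals". Statistical Design and Power gives the method. Engagement and the other candidate mediators are "operationalized as the proportion of possible extended-care sessions attended, adherence to self-monitoring, and changes in dietary intake/physical activity", and they "will be assessed using bootstrapping to estimate confidence intervals around indirect effects". Two are therefore post-randomization levels (attendance proportion, self-monitoring adherence) and two are changes (diet, physical activity).

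The text names no covariates for the indirect effects and does not say from which visit the changes run. The only pre-randomization covariate named for any model is "initial intervention weight loss (as a binary variable representing whether initial weight loss was ≥10% or <10%, used to stratify randomization". It belongs to the primary mixed model and is not carried into the mediation text.

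Elsewhere the protocol acknowledges the associations that matter here. Section 4 (Background) says "Attendance has been consistently associated with long-term weight loss maintenance". Under Intervention and Randomization, the stratification is justified by the "known association between initial weight loss and longer-term maintenance".

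**The concern.** Because "participants will be randomized using a 1:1 allocation scheme", the arm-to-mediator path is a randomized comparison. The mediator-to-weight path is not. People who attended, weighed themselves and logged food reliably before Month 4 will tend to do so afterwards, and will tend to regain less in either arm. A regression of regain on attendance or self-monitoring with no pre-randomization term attributes that tendency to the behaviour. Multiplying the resulting slope by any arm difference in the behaviour gives an indirect effect that need not be causal. The bootstrap deals with sampling error and leaves this bias in place.

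This aim is meant to explain why ADAPTIVE works. The trial could report mediation by a behaviour that has no effect on weight, and later adaptive interventions could be built on it.

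**Working it through.** **The plan's own figure.** Difference 2.5 kg, SD 5.5 kg, power .90 (Statistical Design and Power), with two-sided alpha .05 assumed because none is stated for the primary test: n per group = 2 × (1.960 + 1.282)² × 5.5² / 2.5² ≈ 102, or 103 with the noncentral t. This reproduces the stated 206 completers, and 206 / .80 gives 258 randomized. The plan gives no figure for the mediation analysis.

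**Inputs.** From the documents: 206 completers and SD 5.5 kg. Assumed, because the documents give no values:
- arm shift in the mediator, a = .4 SD
- correlation of the stable trait with the mediator, r = .6
- correlation of the trait with regain, g = -.3
- no effect of the mediator on weight and no direct effect of arm

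**Level mediators, unadjusted.** With a standardized mediator M = a·arm + r·trait + noise, and regain depending on the trait only, the slope of regain on M given arm is r·g = .6 × (-.3) = -.18 SD per SD, or -.18 × 5.5 = -.99 kg per SD. The false indirect effect is .4 × (-.99) = -.396 kg.

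**Level mediators, adjusted.** With k pre-randomization proxies, each as noisy as the mediator and with independent errors, the slope becomes r·g / (1 + k·r²).

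| Proxies | Slope (SD per SD) | False indirect effect (× .4 × 5.5 kg) | Simulated share of 95% intervals excluding zero |
|---|---|---|---|
| 0 | -.18 | -.396 kg | about 59% |
| 1 | -.18 / 1.36 = -.132 | -.291 kg | about 34% |
| 3 | -.18 / 2.08 = -.087 | -.190 kg | about 15-17% for three or four |
| 4 | -.18 / 2.44 = -.074 | -.162 kg | about 15-17% for three or four |

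**Range over the assumed correlations** (a = .4):
- r = .6, g = -.2: false effect .4 × 5.5 × .6 × (-.2) = -.264 kg; about 30% unadjusted, 18% with one proxy, 10% with three or four.
- r = .7, g = -.4: false effect .4 × 5.5 × .7 × (-.4) = -.616 kg; about 81%, 60% and 20-26%.

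**Dependence on the arm shift** (r = .6, g = -.3, unadjusted): at or below about 5% with no shift, about 7% at .1 SD, about 19% at .2 SD.

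**Separate check with a percentile bootstrap** (206 participants, 400 trials per setting; trait loadings on mediator and outcome of .5 and .3, or .7 and .5): unadjusted 29-59% at a shift of .3 SD and 59-95% at .5 SD. With one equally noisy measure the rates were 26-65% and 36-87%. The mean spurious effect fell by about 20-30%, close to the formula's 1 - 1/1.25 = 20% and 1 - 1/1.49 = 33%. At the .3 SD shift the exclusion rate itself hardly moved, so one proxy is a weak remedy.

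**Diet and physical activity.** If change is follow-up minus the Month 4 value and the trait loads equally at both times, the trait cancels: change = a·arm + difference of two noise terms. Its slope with regain is then zero. Simulated false rates are about 3-4% at a shift of .4 SD. Adding the mediator's own baseline undoes this, because change given baseline is algebraically the same regression as follow-up given baseline. The slope returns to r·g / (1 + r²), or -.291 kg in the central case, and the false rate rises to 18-62% across the assumed correlations. If change runs from Month 0 and the trait is not yet expressed there, the unadjusted false rate is 10-42%.

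**The case against.** The strongest reply is that this is one sentence about an exploratory aim. The covariates are unspecified rather than ruled out, and no primary or secondary inference rests on the result. All of that stands and limits the weight of the point. It does not dispose of it, since an analyst who follows the sentence as written fits the unadjusted model.

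A reader might infer several stronger things that the documents do not support:

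- **That all four mediators are exposed alike.** Diet and physical activity are defined as changes, and a change from Month 4 largely removes a stable additive trait. The point is limited to the two level mediators. The unstated baseline visit for the changes is a separate gap.
- **That the trait alone can create mediation.** Randomization balances the trait between arms, so ADAPTIVE must also shift the mediator. The documents give no size for that shift; .4 SD is assumed. Some shift is plausible, since section 4 expects tailoring to improve engagement and adherence. For attendance, the set of possible sessions is monthly in STATIC and trigger-based in ADAPTIVE, so part of a shift could come from the denominator.
- **That the plan has decided against adjustment.** It states no adjustment set, which is a different thing.
- **That adjustment cures the problem.** Rates near 7-20% in the central case with a single covariate need a pre-randomization measure that tracks the trait better than the mediator does (reliability .6-.8 against a trait share of .6² = .36). Nothing in the documents justifies that.

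**Conclusion.** The point holds for the proportion of sessions attended and for self-monitoring adherence. As the method is written, and provided ADAPTIVE shifts the mediator, a behaviour with no effect on weight would show a 95% interval excluding zero in about 59% of trials in the central case (30-81% over the assumed correlations), with a false effect of about -.4 kg. Adjustment with data already collected brings the central case to about 34% with one proxy and 15-17% with three or four. The bias is reduced, not removed.

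These sizes rest on assumed correlations and an assumed .4 SD shift, on a stable additive trait, and on proxies with independent errors. Real proxies that share error would help less. The conclusion does not extend to diet and physical activity measured as change from Month 4. The aim is exploratory, and Aims 1 and 2 are unaffected.

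**What to change.** In the mediation text of Statistical Design and Power:

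1. For session attendance and self-monitoring adherence, fit the mediator and outcome equations with the same pre-randomization covariates, then bootstrap over participants. Use initial-program session attendance, frequency of self-weighing and of calorie logging in weeks 1-16, and continuous percent weight loss from Month 0 to Month 4.
2. Show the unadjusted indirect effect beside the adjusted one, and describe the indirect effect as associational.
3. For diet and physical activity, define change from Month 4, and do not add the mediator's own baseline value as a covariate by default.

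No new data are needed. The smart scale and FatSecret records run through the initial program, Table 1 lists session attendance as assessed continuously (taken here to include the initial group sessions), and percent loss is calculated to determine eligibility for the maintenance trial. The cost is a few sentences, a few degrees of freedom, and indirect effects that will be smaller and less often significant.
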